Primary Aim: To determine if a 48 hour maximum dwell time reduces bacterial contamination and biofilm formation of feeding tubes, feeding tube hubs, and intraluminal fluid in premature VLBW infants. **Primary hypothesis**: Feeding tubes which remain in place 0-48 hours will have less contamination and less biofilm formation compared to those left in place for 7 days.

Aim 2: Compare gastrointestinal microbial dysbiosis and inflammation between Group 1 and Group 2. **Hypothesis:** Infants in Group 1 will have less GI microbial dysbiosis and inflammation compared to Group 2.

Aim 3: Determine the effect of feeding tube dwell time and feeding tube contamination, and biofilm formation on selected health outcomes in premature VLBW infants. **Hypothesis:** Infants in Group 1 will have lower odds for necrotizing enterocolitis and late onset sepsis, and improved nutritional outcomes compared to Group 2.

5. Research Plan:

A randomized controlled trial will be conducted to determine whether feeding tube dwell time is associated with level of feeding tube contamination. Infants will be randomly assigned to have their feeding tubes removed at 0-48 hours or 7 days for the first 4 weeks of life. The feeding tube lumen, interluminal liquid and hub will be analyzed for level of contamination.

Sample and Setting

The proposed study will follow a prospective cohort (N =151) premature VLBW male and female infants for 4 weeks following birth. If the mother is providing breast milk to her infant, she will also be included in the study since she will be providing 2 samples of her breast milk for analysis.

Inclusion criteria are: 1) be born to a mother who is at least 18 years of age and English or Spanish speaking, 2) born at \leq 30 weeks 3) have a birthweight \leq 1500 grams, 4) be born to a mother who is COVID Negative, 5) have a feeding tube placed within 24 hours of birth and 5) be expected to require a feeding tube for 4 weeks following birth.

Exclusion criteria are: 1) Infant with known congenital GI anomalies, (2) are not expected to live, or (3) Infants will be withdrawn from the study if they require abdominal surgery for GI morbidities.

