Sample Size Determination/Power Analysis: The primary aim of this study is to test for associations between feeding tube dwell time and the bacterial load present in the feeding tube. Pilot study results were used to estimate variance for the log transformed values of bacterial load observed in cultures. The study employs a repeated measures design, with measurements performed on each neonate each week of the 4 week study duration. For the primary bacterial contamination aim, each measurement consists of measures from 5 individual feeding tube sections for 5 individual colony types, providing a total of 100 within-subjects data points per neonate. Given the repeated measures design and the incorporation of selected covariates, a Generalized Linear Mixed Model (GLMM) analysis is planned for the primary aim. The data derived from the pilot study of 31 feeding tubes informed the covariance structure and means vectors for entry into PASS 14's procedure which estimates mixed models power using simulation. Using a .005 level of significance (in recognition of the multiple inferential tests), 400 simulation samples, a minimum detectable difference of 3.0 (natural log transformed colony forming units), and employing the pilot data to inform mean vectors and the unstructured covariance matrix for the simulations, the lower 99% confidence limit for power is .97 for the Dwell Group by Colony Type interaction, which is of primary interest. To accommodate the anticipated 10% loss due to surgery or death, 134 neonates will be enrolled. If mothers are providing breast milk samples, 151 mothers would also be enrolled.

Standard Infant Feeding Protocol

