Following consent, data including gestational age, chronologic age, birth weight, race, gender, date and time of sample collection, feeding tube dwell time, duration of antibiotic therapy since birth, episodes of sepsis, other medications, mode of delivery, and mode and type of feeding will be obtained from the EMR. Other data including incidence of stage 2 or greater necrotizing enterocolitis; episodes of presumed or culture proven late onset sepsis (occurring > 3 days of life); days to discharge; nutritional outcomes, including weekly enteral intake, days to full enteral feedings (120 mL/kg/d),(150ml/kg/day), hours of parenteral nutrition, evidence of PNALD (level of direct bilirubin, alkaline phosphatase, aspartate aminotransferase (AST) and alanine aminotransferase (ALT); growth indices (weekly weight, head circumference and length); and hours with a central venous line will be collected.

Infants in both groups will have a bedside sign and EPIC note stating which group they are assigned to and when they are scheduled for feeding tube replacement. Infants will have their feeding tubes replaced 0-48h (Group 1) and every 7 days (Group 2). At the designated time, the feeding tube will be replaced by either the bedside nurse or the research coordinator (an experienced NICU nurse) using the NICU's standard method of feeding tube insertion.

All tubes will be adhered to the infant's face using the same procedure designed to decrease the risk of feeding tube dislodgement and protect skin integrity. The method of tube securement will be approved by NICU management/staff and comply with NICU skin care guidelines. The orogastric tubes will be taped to the chin from the middle of the mouth and nasogastric tubes will be taped under the lateral edge of nares. The research team will check the security of the tube adherence 3x per week and re-secure as necessary. On the day that the study feeding tube is scheduled to be removed, the research coordinator will coordinate with the bedside nurse when the feeding tube will be removed and replaced. In the event the infant has a Replogle tube instead of a feeding tube on lab collection day, the Replogle tube will collected. At the designated time, the feeding tube or Replogle will be removed and immediately placed in a sterile Ziploc bag and placed on ice for immediate transfer to laboratory by member to research team.

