1.PNALD	Liver function tests (level of direct bilirubin, alkaline phosphatase, AST and ALT)	Weekly or biweekly for 6 weeks Peak alkaline phosphatase and Peak direct bilirubin for up to 20 weeks or discharge
2. Hours of central venous line access	Number of hours infant has a central venous line	Daily for up to 20 weeks
3. Growth indices	Weight, length, and head circumference	Daily for 4 weeks and at discharge
4. Episodes of late onset sepsis	Episodes of culture proven or presumed sepsis (treated with \geq 3 days of antibiotics but with negative cultures)	Daily from birth up to 20 weeks
5.Episodes of NEC	Episodes of radiologic or surgical evidence of NEC	All incidences for up to 20 weeks
6. Length of hospital stay	Days infant remains in hospital	From birth until discharge
Covariates (1-5) below		
1. Gastric pH	pH of gastric aspirates, use of medications which affect gastric pH	Gastric pH analysis will be done weekly, information regarding medications will be collected during the 4 weeks study period
2. Oropharyngeal swabs	Time of last feed, oral medications	Sputum samples weekly for 4 weeks
3.Analysis of maternal breast milk or donor milk	Microbiota and metagenomic sequencing	At week 1 and week 4

4. Nutritional data	Medications and disease processes associated with decreased intestinal motility, episodes and duration of kangaroo care	Upon entry into study and for 4 active weeks.

visually inspected before data entry. A manual comparison of randomly selected data hardcopy forms with data output listing generated from the study database will be performed, and consistency checks will be generated by SQL or SAS programs as part of data cleaning procedures. The system will assign a global unique identifier to each enrolled subject that will serve as the subject id. Study case report forms (CRFs) will be maintained in study specific folders and when CRFs not actively being processed, will be secured in locked file cabinets. In addition to the use of passwords and other security measures, all documents containing identifying information are considered confidential materials and will be safeguarded. Data to be collected are found in Table 3. Data collected in REDCap will be shared with an outside affiliated researcher at Old Dominion University for secondary data analysis. All data sets shared will be verified with CTSI REDCap, before giving outside researcher access.

7. Possible Discomforts and Risks:

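### Late onset sepsis combines culture-proven episodes with presumed episodes defined by antibiotic duration, group is openly displayed, and no analysis by component is pre-specified

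*Combined protocol and SAP*

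**What the plan says.** The data table under Data Entry and Management has a single row for late onset sepsis: "Episodes of culture proven or presumed sepsis (treated with" at least "3 days of antibiotics but with negative cultures"). Its timing is "Daily from birth up to 20 weeks". The Procedure section groups the two kinds in the same way: "episodes of presumed or culture proven late onset sepsis (occurring > 3 days of life"). Neither place gives a clinical-sign or laboratory criterion for a presumed episode.

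The Procedure section also says: "Infants in both groups will have a bedside sign and EPIC note stating which group they are assigned to". The documents describe no blinding of staff and no blinded classification of outcomes.

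Aim 3 states a directional hypothesis: "Infants in Group 1 will have lower odds for necrotizing enterocolitis and late onset sepsis". The Statistical Analysis section sets out a general mixed-model strategy for all outcomes. It does not say whether the two kinds of sepsis will be modelled together or apart, and it names no sensitivity analysis on culture-proven episodes.

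**The concern.** A culture-proven episode needs a positive laboratory result. A presumed episode, as defined here, needs only that the clinician keeps antibiotics going for at least 3 days after cultures are negative. That is a judgement, made by people who know the infant's group in a trial whose stated expectation is fewer complications with shorter dwell. If staff are somewhat readier to stop antibiotics in Group 1, or to continue them in Group 2, the count of presumed episodes moves although infection has not.

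At stake is the sepsis part of Aim 3. If only the combined outcome is analysed, a lower odds in Group 1 could reflect less infection, different labelling, or both, and that result alone could not separate them. Sepsis is among the complications that the Background section says the research aims to reduce, so a favourable finding would be noticed.

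**Working it through.** There is no plan figure to reproduce: the documents give no sepsis rate, effect size or power for Aim 3. What follows is an illustration on assumed rates.

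**Inputs from the documents.** The sepsis definition and the open display of group are as quoted above. Allocation is random between two groups ("Infants will be randomly assigned to have their feeding tubes removed at 0-48 hours or 7 days") with no ratio given, so 1:1 is assumed. On numbers, the power section says: "To accommodate the anticipated 10% loss due to surgery or death, 134 neonates will be enrolled". That leaves 134 × 0.90 = 120.6, or about 60 per group. The Sample and Setting section gives 151 infants instead; the odds ratios below do not depend on the number.

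**Assumptions.** Each infant counts once. There is no true effect. Culture-proven sepsis occurs in a fraction c of infants in both groups, with c = 10% or 20%. Presumed sepsis occurs in other infants: a fraction p of Group 2 (20% or 30%), and p(1 − s) of Group 1, where s is the relative reduction in labelling.

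**Formula.** Group 2 pooled rate b = c + p. Group 1 pooled rate a = c + p(1 − s). Pooled odds ratio = [a/(1 − a)] / [b/(1 − b)].

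**Results for s = 25%.**

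| p | c | a | b | Pooled odds ratio |
|---|---|---|---|---|
| 20% | 10% | 25% | 30% | (.25/.75)/(.30/.70) = 0.78 |
| 20% | 20% | 35% | 40% | (.35/.65)/(.40/.60) = 0.81 |
| 30% | 10% | 32.5% | 40% | (.325/.675)/(.40/.60) = 0.72 |
| 30% | 20% | 42.5% | 50% | (.425/.575)/(.50/.50) = 0.74 |

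**Varying the shift.** With s = 10% and p = 20%, the rates are 28% v 30% (odds ratio 0.91) and 38% v 40% (0.92). With s = 10% and p = 30%, they are 37% v 40% (0.88) and 47% v 50% (0.89). With s = 0 the odds ratio is 1.

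**Chance of a false significant result.** Take 60 per group and a two-sided 5% two-proportion test. For 30% v 25%, the standard error under the null is √(.275 × .725 × 2/60) = 0.0815 and the unpooled one is √(.30 × .70/60 + .25 × .75/60) = 0.0814. The rejection probability is Φ((.05 − 1.96 × .0815)/.0814) + Φ((−.05 − 1.96 × .0815)/.0814) = 0.089 + 0.005, or about 9%. The same calculation gives about 9% for 40% v 35%, 14% for 40% v 32.5% and 13% for 50% v 42.5%. With s = 10% all four cases lie near 6%. The nominal level is 5%, and a culture-proven analysis stays there under these assumptions.

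**Precision of the culture-proven analysis.** By the same method at 60 per group, power to detect a true halving is about 18% from a 10% rate and 33% from a 20% rate.

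**The case against.** The case on the other side has several parts.

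- *The table lists data to collect; it is not an analysis specification.* This stands. A pooled analysis is inferred from the single row and the matching Procedure text. The supportable point is that no analysis by component is pre-specified.
- *Nothing in the documents supports a 25% shift, or its direction.* This also stands. The 25% is an assumption, and a 10% shift leaves an odds ratio of 0.88-0.92 and little excess false-positive risk at this sample size. Episodes late in the 20-week window, after the 4 weeks of assigned dwell, may also be less exposed to knowledge of group.
- *The size can be overstated.* A reader might work from presumed sepsis alone and infer odds ratios of (.15/.85)/(.20/.80) = 0.71 or (.225/.775)/(.30/.70) = 0.68. Those do not describe the recorded outcome, because culture-proven infants, unchanged in both groups, dilute the shift.
- *Culture-proven sepsis is not free of the problem.* True: unblinded staff presumably also decide when to draw cultures. It is less exposed, since a positive result is still needed.
- *Culture-proven events are few.* True, as the 18-33% power shows. A reader might infer that culture-proven sepsis should be the only outcome on which the sepsis hypothesis is judged. The documents do not require that trade, and it would leave the hypothesis close to untestable.
- *Blinding staff is hardly feasible when the bedside nurse may change the tube.* Agreed. That is a reason to plan the analysis for open labelling.

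**Conclusion.** The point holds as a modest, inexpensive gap in the plan for a secondary aim. The recorded sepsis outcome includes a component that rests on treatment decisions made with knowledge of group, and the plan does not commit to looking at the components separately. A labelling difference could therefore produce an apparent benefit. On the stated assumptions (no true effect, 25% less presumed labelling in Group 1), the pooled odds ratio would be about 0.78-0.81 with presumed sepsis at 20% and 0.72-0.74 at 30%, and closer to 1 for a smaller shift.

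A reader might infer that such bias will occur or that the pooled outcome is invalid. The documents show only that it could occur and that the plan has no means of recognising it. Nor does the point reach the primary aim, which rests on bacterial load measured on the tubes in the laboratory.

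**What to change.** In the data collection form, record culture-proven and presumed late onset sepsis as separate items. Classifying an episode already requires the culture result and the length of the antibiotic course, so this should add little work. The table lists antibiotic tracking for 6 weeks but sepsis for 20, so the form should hold both items for later episodes too.

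In the Statistical Analysis section, pre-specify a culture-proven late onset sepsis analysis alongside the pooled one. State that a sepsis benefit under Aim 3 will be claimed only if both point the same way. If only the pooled outcome differs, report the difference as possibly due to open-label labelling.

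The cost is some plan wording, one more model and a culture-proven estimate that will be imprecise. The safeguard is partial. With no true effect, the culture-proven estimate will favour Group 1 by chance about half the time, so its confidence interval should be shown beside the pooled one. Classification of episodes against pre-set criteria by an assessor unaware of group would help further if resources allow. None of this changes clinical care.
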